11.1.4 Response Criteria

11.1.4.1 Evaluation of Target Lesions

Complete Response (CR): Disappearance of all target lesions. Any pathological lymph nodes (whether target or non-target) must have reduction in short axis to <10 mm.

Partial Response (PR): At least a 30% decrease in total tumor measurement.

Progressive Disease (PD): At least a 20% increase in the total tumor measurement, taking as reference the smallest sum on study (this includes the baseline sum if that is the smallest on study). In addition to the relative increase of 20%, the sum must also demonstrate an absolute increase of at least 5 mm. (Note: the appearance of one or more new lesions is also considered progressions).

Stable Disease (SD): Neither sufficient shrinkage to qualify for PR nor sufficient increase to qualify for PD, taking as reference the smallest sum diameters while on study.

11.1.4.2 Evaluation of Non-Target Lesions

Complete Response (CR): Disappearance of all non-target lesions and normalization of tumor marker level. All lymph nodes must be non-pathological in size (<10 mm short axis).

Note: If tumor markers are initially above the upper normal limit, they must normalize for a patient to be considered in complete clinical response.

Non-CR/Non-PD: Persistence of one or more non-target lesion(s) and/or maintenance of tumor marker level above the normal limits.

Progressive Disease (PD): Appearance of one or more new lesions and/or *unequivocal progression* of existing non-target lesions. *Unequivocal progression* should not normally trump target lesion status. It must be representative of overall disease status change, not a single lesion increase.

Although a clear progression of "non-target" lesions only is exceptional, the opinion of the treating physician should prevail in such circumstances, and the progression status should be confirmed at a later time by the review panel (or Principal Investigator).

11.1.4.3 Evaluation of New Lesions

The finding of a new lesion should be unequivocal (i.e. not due to difference in scanning technique, imaging modality, or findings thought to represent something other than tumor (for example, some 'new' bone lesions may be simply healing or flare of pre-existing lesions). However, a lesion identified on a follow-up scan in an anatomical location that was not scanned at baseline is considered new and will indicate PD. If a new lesion is equivocal (because of small size etc.), follow-up evaluation will clarify if it truly represents new disease and if PD is confirmed, progression should be declared using the date of the initial scan on which the lesion was discovered. Timing of the follow up evaluation should be performed at the discretion of the treating investigator and no more than 8 weeks following the date of the imaging that identified the potential new lesion.

11.1.4.4 Evaluation of Best Overall Response

The best overall response is the best response recorded from the start of the treatment until disease progression/recurrence (taking as reference for progressive disease the smallest measurements recorded since the treatment started). The patient's best response assignment will depend on the achievement of both measurement and confirmation criteria.

For Participants with Measurable Disease (*i.e.*, Target Disease)

Table 8: Criteria for Participants with Measurable Disease									
Target Lesions	Non-Target Lesions	New Lesions	Overall Response	Best Overall Response when Confirmation is Required					
CR	CR	No	CR	≥4 wks Confirmation*					
CR	Non-CR/Non- PD	No	PR						
CR	Not evaluated	No	PR	>4 wks Confirmation**					
PR	Non-CR/Non- PD/not evaluated	No	PR						
SD	Non-CR/Non- PD/not evaluated	No	SD	Documented at least once ≥4 wks from baseline**					
PD	Any	Yes or No	PD						
Any	PD***	Yes or No	PD	no prior SD, PR or CR					
Any	Any	Yes	PD]					

* Only for non-randomized trials with response as primary endpoint.

** In exceptional circumstances, unequivocal progression in non-target lesions may be accepted as disease progression.

Note: Participants with a global deterioration of health status requiring discontinuation of treatment without objective evidence of disease progression at that time should be reported as "*symptomatic deterioration*." Every effort should be made to document the objective progression even after discontinuation of treatment.

For Participants with Non-Measurable Disease (i.e., Non-Target Disease)

Table 9: Criteria for Participants with Non-Measurable Disease							
Non-Target Lesions	New Lesions	Overall Response					
CR	No	CR					
Non-CR/non-PD	No	Non-CR/non-PD*					
Not all evaluated	No	not evaluated					
Unequivocal PD	Yes or No	PD					
Any	Yes	PD					
* 'Non-CR/non-PD' is preferred over 'stable disease' for non-target disease since SD is							

increasingly used as an endpoint for assessment of efficacy in some trials so to assign this category when no lesions can be measured is not advised

11.1.5 Duration of Response

Duration of overall response: The duration of overall response is measured from the time measurement criteria are met for CR or PR (whichever is first recorded) until the first date that recurrent or progressive disease is objectively documented (taking as reference for progressive disease the smallest measurements recorded since the treatment started, or death due to any cause. Participants without events reported are censored at the last disease evaluation).

Duration of overall complete response: The duration of overall CR is measured from the time measurement criteria are first met for CR until the first date that progressive disease is objectively documented, or death due to any cause. Participants without events reported are censored at the last disease evaluation.

Duration of stable disease: Stable disease is measured from the start of the treatment until the criteria for progression are met, taking as reference the smallest measurements recorded since the treatment started, including the baseline measurements.

11.1.6 Progression-Free Survival

Overall Survival: Overall Survival (OS) is defined as the time from randomization (or registration) to death due to any cause, or censored at date last known alive.

Progression-Free Survival: Progression-Free Survival (PFS) is defined as the time from randomization (or registration) to the earlier of progression or death due to any cause. Participants alive without disease progression are censored at date of last disease evaluation.

Time to Progression: Time to Progression (TTP) is defined as the time from randomization (or registration) to progression, or censored at date of last disease evaluation for those without progression reported.

11.1.7 Response Review

Evaluation of scans will be done centrally at the DFCI using the Tumor Imaging Metrics Core.

12. DATA REPORTING / REGULATORY REQUIREMENTS

Adverse event lists, guidelines, and instructions for AE reporting can be found in Section 7 (Adverse Events: List and Reporting Requirements).

12.1 Data Reporting

12.1.1 Method

The Office of Data Quality (ODQ) will collect, manage, and perform quality checks on the data for this study.

12.1.2 Responsibility for Data Submission

Investigative sites within DF/HCC or DF/PCC are responsible for submitting data and/or data forms to the ODQ according to the schedule set by the ODQ.

12.2 Data Safety Monitoring

The DF/HCC Data and Safety Monitoring Committee (DSMC) will review and monitor toxicity and accrual data from this study. The committee is composed of clinical specialists with experience in oncology and who have no direct relationship with the study. Information that raises any questions about participant safety will be addressed with the Overall PI and study team.

The DSMC will review each protocol up to four times a year or more often if required to review toxicity and accrual data. Information to be provided to the committee may include: up-to-date participant accrual; current dose level information; DLT information; all grade 2 or higher unexpected adverse events that have been reported; summary of all deaths occurring with 30 days of intervention for Phase I or II protocols; for gene therapy protocols, summary of all deaths while being treated and during active follow-up; any response information; audit results, and a summary provided by the study team. Other information (e.g. scans, laboratory values) will be provided upon request.

13. STATISTICAL CONSIDERATIONS

We will employ a Simon's 2-stage design to test the hypothesis that durvalumab and tremelimumab improve response rates in this patient population to 35%, compared to a historical control rate of 16%. In the first stage we will enroll 19 patients, and if 4 or more patients among those 19 respond to therapy (with either a complete or partial response), we will open the 2nd stage of accrual to enroll an additional 21 patients, making a total sample size of 40 patients. If fewer than 4 patients experience a response in the first stage then the study will be stopped. In order to declare study success, a total of 10 or more responses must be observed among all 40 study participants. This design has a 0.64 probability of stopping early under the null, and has 90% power while maintaining an overall one-sided type I error rate of 0.08.

Statistical Analysis Plan for Correlative Studies:

Data from correlative studies will be summarized using descriptive statistics. Associations

between immune cell subsets, immune marker expression, and the characteristics of the PBMCs will be compared to clinical outcome, will be summarized by descriptive methods, and may be explored graphically.

We assume that 80% of patients (n=32) will be successfully biopsied at multiple time points and have tumors that yield valid results from the laboratory.

When comparing baseline, on-treatment, and time of progression genomic and immune results, it is of interest to identify new alterations that were not present at baseline. Initial analyses of these data will utilize tests for association comparing the frequency of a particular genomic or immune aberration at baseline, on-treatment, and at progression (for example, using McNemar's test) and association between alterations and baseline characteristics (for example, using Fisher's exact test). For non-normal distributions (% T-cell infiltrate), we will explore associations with the presence or absence of a genomic or immune feature using non-parametric analysis for subgroup comparisons (Wilcoxon rank-sum or Kruskall-Wallis). Fisher's exact test will be used for discrete comparisons of categorical immune and clinical variables (such as PD-L1 positive vs. negative). More sophisticated analyses may include multivariable logistic regression modeling and/or competing risks analysis, however it is expected that analyzable results will not be obtained from all patients (either due to things like assay failure, inability to biopsy at progression due to poor patient health, etc).

With at least 32 patients included in the correlative analysis, this sample size provides 84% power to detect differences in the rate of another binary variable (such as baseline characteristics or abnormality) with frequencies of 8% and 60%, respectively, while testing with a one-sided 0.10-level Fisher's exact test; this also assumes that the underlying prevalence of the genomic marker is 50%, thus splitting the cohort into two groups with 16 patients in each. It is worth noting that the Fisher's test for association between the presence/absence of baseline samples and resistant samples assumes independence between those samples. Given what is known about tumor heterogeneity, the likelihood that the cancer may be altered genomically over time and due to therapy, and the low chance that the same area of a patient's tumor will be biopsied at both time points, this seems like a reasonable assumption.

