9.1.2 Fresh Tumor Biopsies

Mandatory pre- and on-treatment fresh tumor biopsies will be obtained from patients enrolling to the trial. In the event the biopsy is not clinically feasible in the opinion of the treating investigator or interventionalist performing the procedure, exceptions to one or both fresh biopsy requirements are possible after discussion with the principal investigator.

The pre-treatment biopsy should be obtained following consent and prior to the first dose of any study medication (prior to Cycle 1 Day 1). The on-treatment biopsy may be obtained anytime between Cycle 2 Day 1 (after completion of the study medication infusions) to Cycle 2 Day 8.

An additional optional biopsy at the time of disease progression will also be offered to patients if deemed clinically feasible by the treating investigator. In patients undergoing re-treatment with tremelimumab, the time of progression biopsy may be obtained either prior to the initiation of re-treatment or upon progression following re-treatment. Preferably, time of progression biopsies should be obtained prior to the initiation of another cancer treatment. However, in the event that it is not possible to perform the biopsy before another treatment is begun, the biopsy can be obtained up to 60 days after the last dose of study medication.

Pre- and on-treatment core biopsy samples a minimum of 2 cores should be collected, if clinically feasible. A 16-18 gauge needle are preferable, but a 20 gauge core needle biopsy is also acceptable. For more information, please refer to the Thoracic Oncology Program 16-549 Biopsy Collection Guidelines. In the event that not enough tissue is obtained, priority should go to immune profiling.

If a core biopsy is judged to be too unsafe or difficult for the participant in the opinion of the treating investigator, a fine needle aspirate (FNA) or cytology sample can also be collected. The goal for a thoracentesis or paracentesis procedure will be 500 - 1000 mL collected in a standard collection tube. The goal for an FNA will be three distinct passes. Less than the goal amount of tissue is acceptable for any of the biopsy collection methods, and should be based upon the clinical judgment of the treating investigator and the clinician performing the procedure.

All tumor biopsy samples should be labeled with the protocol number, study subject number, date of collection, and identified as either "pre-treatment," "on-treatment," or "time of progression."

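### The correlative sample of 32 is the expected yield if stage 2 completes, not a minimum; a stage-1 stop leaves about 15 patients and no stated power

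*Combined protocol and SAP*

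**What the plan says.** All of this is in Section 13 unless noted.

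- Two-stage design: "In the first stage we will enroll 19 patients". A further 21 are added only if 4 or more respond, "making a total sample size of 40 patients". Otherwise: "If fewer than 4 patients experience a response in the first stage then the study will be stopped".
- On the chance of stopping: "This design has a 0.64 probability of stopping early under the null", the null response rate being 16% and the target 35%.
- Correlative sample size: "We assume that 80% of patients (n=32) will be successfully biopsied at multiple time points".
- Correlative power: the sentence beginning "With at least 32 patients included in the correlative analysis" claims 84% power for 8% versus 60% with a one-sided 0.10-level Fisher's exact test. It assumes a marker prevalence of 50%, hence 16 patients per group.
- Section 13.3 labels subset analyses, correlatives included, as exploratory.

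No correlative sample size or power is given for a trial that stops after stage 1.

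**The concern.** The 32 enters as an assumed yield and reappears, in the power sentence, as a floor. The two uses conflict, because 80% of 40 presupposes full accrual while the design allows the trial to end at 19. After such a stop 32 cannot be reached even if every patient yields usable tissue.

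What is at stake is how Section 13 is read. It quotes one power figure without tying it to stage 2 opening. Under the plan's own null, the smaller sample is the more likely outcome, and a reader of the eventual correlative results would have no prespecified statement of what that sample could detect. Checking the figure also shows a second problem: the 84% does not follow from the inputs beside it.

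**Working it through.** **Inputs (Section 13).** Stage 1 n = 19; total n = 40; stop if 3 or fewer respond; response rates 16% and 35%; evaluable fraction 0.80; rates compared 0.08 and 0.60; one-sided alpha 0.10; Fisher's exact test; two equal groups; stated power 84%.

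**Step 1: the stated power.** Exact power is the sum, over all a from 0 to n1 and b from 0 to n2, of Bin(a; n1, 0.08) × Bin(b; n2, 0.60), counting only tables whose Fisher p-value is at or below alpha. With n1 = n2 = 16:

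- one-sided 0.10 (as stated): 95.9%
- one-sided 0.05 or two-sided 0.10: 91.3%
- two-sided 0.05: 83.95%

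The 84% is therefore not reproduced at the stated level. It is reproduced at two-sided 0.05.

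**Step 2: the chance of a stage-1 stop.** P(X ≤ 3) for X ~ Bin(19, p):

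- p = 0.16: 0.0364 + 0.1318 + 0.2259 + 0.2439 = 0.638, matching the stated 0.64
- p = 0.35: 0.0003 + 0.0029 + 0.0138 + 0.0422 = 0.059

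The overall design also checks: type I error 0.082 and power 0.901, against the stated 0.08 and 90%.

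**Step 3: evaluable patients.**

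- Full accrual: 0.80 × 40 = 32
- Stage-1 stop: 0.80 × 19 = 15.2, about 15
- Expected number at 16%: 0.80 × (19 × 0.638 + 40 × 0.362) = 21.3
- Expected number at 35%: 0.80 × (19 × 0.059 + 40 × 0.941) = 31.0

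**Step 4: power in each case, 8% versus 60%, exact Fisher.** For 15 patients the closest to an even split is 7 and 8, and the answer depends on which group has the low rate.

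| Evaluable | Split (low-rate / high-rate) | One-sided 0.10 | Two-sided 0.05 |
|---|---|---|---|
| 32 | 16 / 16 | 95.9% | 83.95% |
| 15 | 8 / 7 | 63.4% | 53.2% |
| 15 | 7 / 8 | 67.2% | 44.8% |
| 19 (every patient evaluable) | 10 / 9 | 78.0% | 61.0% |
| 19 (every patient evaluable) | 9 / 10 | 80.8% | 55.8% |

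At the stated level, the shortfall with 15 patients is 17 to 21 points against the printed 84% (84 − 67 and 84 − 63). Against the 95.9% that the stated inputs actually give, it is 29 to 33 points (95.9 − 67.2 and 95.9 − 63.4). Even a 100% yield from 19 patients stays below 84%.

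**Step 5: is 32 a floor at full accrual?** Assume, as the documents do not, that each of 40 patients is independently evaluable with probability 0.80. Then P(32 or more) = 0.593. Including the stopping rule, it is 0.362 × 0.593 = 0.21 at a 16% response rate and 0.941 × 0.593 = 0.56 at 35%.

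**The case against.** The strongest reply is that the power sentence is conditional: if at least 32 patients are included, power is as given. Section 13 introduces the 80% as an assumption, and the correlative text says that some patients will not yield analyzable results, naming assay failure and patients too ill for a progression biopsy. Quoting power at planned accrual is common, and no decision depends on this figure. Much of this stands. The uncertainty about tissue yield is disclosed, and 0.8 × 40 = 32 is correct arithmetic. What is not disclosed is that the design itself can end at 19, where the condition cannot be met.

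Two stronger readings are tempting, and the documents support neither.

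- A reader might infer that 32 is a ceiling. It is not. The maximum is 40, and a yield above 80% would exceed 32. Section 9.1.1 also collects archival tissue from all enrolled patients where available, and Section 2.6.1 expects most to have genomic profiling already, so some baseline marker analyses could include more than 32.
- A reader might point to the progression biopsy (Section 9.1.2: "An additional optional biopsy at the time of disease progression will also be offered to patients") as further proof that 32 is out of reach. That is weak support. The 80% already allows for failed or missing samples, and the pre- and on-treatment biopsies, mandatory unless not feasible, can supply multiple time points. The power sentence concerns a marker against another binary variable and need not involve progression tissue.

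**Conclusion.** The point holds as a misstated sample size and an unreconciled power figure. The 32 is the expected yield if stage 2 completes. If the trial stops after stage 1, about 15 evaluable patients are expected, and power for the plan's own example is about 63–67% at one-sided 0.10, or 45–53% at two-sided 0.05. Separately, 16 per group at one-sided 0.10 gives about 96%, so the printed 84% and the printed alpha do not belong together.

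These results rest on the plan's 80% yield applying equally after an early stop, a marker prevalence of 50% giving a near-even split, and the 8% versus 60% contrast. With a random 50% split, power for 15 patients averages 64.2%, so the near-even split is not driving the result.

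The importance is small: the correlative analyses are exploratory, and the two-stage response-rate design reproduces as stated. The documents also give no basis for arguing that the early-stop case is the one where correlative power matters most.

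**What to change.** In Section 13, replace the opening clause of the correlative power sentence with wording such as: *If stage 2 completes, about 32 evaluable patients are expected; if the study stops after stage 1, about 15.* An upper-limit phrasing (up to 32) should be avoided, since it would replace a wrong floor with a wrong cap.

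Then state power for both cases under one alpha level:

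- one-sided 0.10: about 96% and 63–67%
- two-sided 0.05: about 84% and 45–53%

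Keeping one-sided 0.10 would agree with the level Section 13.3 sets for Fisher's exact tests of categorical data.

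The change is to wording only, with no added patients, biopsies or procedures. The cost is a less favourable stated figure for the early-stop case. A separate sample size for the baseline-to-progression comparison would be a further step: it needs an uptake rate for the optional progression biopsy, which the documents do not give, and this correction does not depend on it.

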13.3 Analysis of Primary and Secondary Endpoints

The primary and secondary analyses will include all eligible patients who started assigned therapy. The exception to this includes the planned analysis of toxicity data, which will include all patients who received study drug regardless of eligibility. Response will be assessed using the modified RECIST criteria for mesothelioma; toxicity will be graded using CTCAE v. 4.03.

For the analysis of the response efficacy measures, participants will be censored if they are alive and without disease progression at the date of the last disease evaluation. In the case of OS, participants will be censored if they are living at the date last known alive.

Time-to-event data, such as PFS and OS, will be estimated using the Kaplan-Meier method, and Cox proportional hazards models will be used to estimate hazard ratios. Comparisons of groups will be made using the logrank test and Cox modeling.

Categorical data, such as response rates (CR+PR) and toxicity, will be compared using Fisher's exact tests with a one-sided type I error rate of 10%; multivariable logistic regression modeling will be used to adjust for the effect of any covariates that are associated with these categorical outcomes. Though none are currently planned, any continuous outcomes will be analyzed using Wilcoxon rank sum test, and multivariable linear regression models may be used to adjust for multiple associations with outcome.

Modeling procedures will implement backward selection; variables significant at the 0.10 level in the univariate setting will be chosen for inclusion in an initial full model, and at each step the least significant variable will be removed from the model. Only those covariates with p<0.05 will remain in any final models, unless there are factors identified by the study team as crucial to model interpretation.

Point estimates of all endpoints will be accompanied by the corresponding two-sided 80% confidence intervals. The method of Atkinson and Brown will be used for the estimation of the confidence interval for response.

In the event that there are missing data, no imputation of the missing data will be conducted. We will assume that data are missing at random and will conduct all analyses as originally planned because we do not anticipate an excess of missing data.

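### The 84% power stated for the correlative Fisher's exact test does not follow from its own inputs: as specified the power is about 96%, and 84% is what a two-sided 0.05 test gives

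*Combined protocol and SAP*

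**What the plan says.** Section 13 (Statistical Considerations), under the analysis plan for correlative studies, gives a complete power statement.

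- Number of patients: "We assume that 80% of patients (n=32) will be successfully biopsied at multiple time points", that is, 80% of the 40 planned.
- Groups: a marker prevalence of 50%, "thus splitting the cohort into two groups with 16 patients in each".
- Rates to be distinguished: "with frequencies of 8% and 60%, respectively".
- Test: "while testing with a one-sided 0.10-level Fisher's exact test".
- Result: "this sample size provides 84% power to detect differences in the rate of another binary variable".

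Section 13.3 (Analysis of Primary and Secondary Endpoints) repeats the level for categorical data such as response and toxicity: Fisher's "exact tests with a one-sided type I error rate of 10" percent.

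**The concern.** A difference of 52 percentage points is very large for two groups of 16, and a one-sided 0.10 test is lenient. Power of only 84% under those conditions looks too low. If so, the printed power and the printed test do not describe the same analysis.

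This is the plan's only numerical statement of what the correlative analysis can detect, and that analysis relies on the pre-treatment and on-treatment biopsies that Section 9.1.2 makes mandatory where feasible. A reader would conclude that only differences of about 50 points can be found with reasonable power. The mismatch also leaves the intended level in doubt. With 32 patients, the choice between one-sided 0.10 and two-sided 0.05 can decide whether an association is reported as positive.

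**Working it through.** **Inputs, all from Section 13.** n = 16 per group; rates 0.08 and 0.60; Fisher's exact test; one-sided level 0.10; stated power 84%.

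**Method.** Let a be the count in the 8% group and b the count in the 60% group. For each pair (a, b), the one-sided Fisher p-value is the hypergeometric tail probability of b or more events in the second group, given a + b events among 32 patients. Power is the sum of Bin(a; 16, 0.08) × Bin(b; 16, 0.60) over all pairs with p ≤ alpha.

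**Example of the rejection rule, a = 1.** The p-value is [C(16, b+1) + 16 × C(16, b)] / C(32, b+1).

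- b = 5: (8,008 + 16 × 4,368) / 906,192 = 77,896 / 906,192 = 0.086
- b = 6: (11,440 + 16 × 8,008) / 3,365,856 = 139,568 / 3,365,856 = 0.041
- b = 7: (12,870 + 16 × 11,440) / 10,518,300 = 195,910 / 10,518,300 = 0.019

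So with one event in the first group, 5 events in the second are enough at one-sided 0.10, but 7 are needed at one-sided 0.025.

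**Full sum.** For each a, the table gives the smallest b that rejects, the probability of reaching it under a 60% rate, and the contribution to power.

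| a | P(a) | b needed, 0.10 | P(reach) | contribution | b needed, 0.025 | P(reach) | contribution |
|---|---|---|---|---|---|---|---|
| 0 | 0.2634 | 4 | 0.9991 | 0.2631 | 5 | 0.9951 | 0.2621 |
| 1 | 0.3665 | 5 | 0.9951 | 0.3647 | 7 | 0.9417 | 0.3451 |
| 2 | 0.2390 | 7 | 0.9417 | 0.2251 | 9 | 0.7161 | 0.1711 |
| 3 | 0.0970 | 8 | 0.8577 | 0.0832 | 10 | 0.5272 | 0.0511 |
| 4 | 0.0274 | 9 | 0.7161 | 0.0196 | 11 | 0.3288 | 0.0090 |
| 5 | 0.0057 | 10 | 0.5272 | 0.0030 | 12 | 0.1666 | 0.0010 |
| 6 | 0.0009 | 11 | 0.3288 | 0.0003 | 13 | 0.0651 | 0.0001 |
| Sum | | | | **0.9590** | | | **0.8395** |

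Terms with a ≥ 7 add less than 0.0001.

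**Power by level (16 versus 16, 8% versus 60%).**

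| Level | Exact power |
|---|---|
| One-sided 0.10 (as stated) | 95.9% |
| One-sided 0.05, or two-sided 0.10 | 91.2% |
| One-sided 0.025, or two-sided 0.05 | 83.9% |

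The two-sided results are the same whether the p-value is formed by the minimum-likelihood rule or by doubling.

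**Can anything else at one-sided 0.10 produce 84%?**

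- Rounding of the rates: 8.5% versus 59.5% gives 95.1%, and 7.5% versus 60.5% gives 96.6%. No.
- Random split of the 32 patients by a 50% marker: 95.5%. No.
- Normal approximation: 98.5% uncorrected, 95.9% with continuity correction. No.
- Uneven fixed split: only near 6 or 7 versus 26 or 25 (82.3% to 86.7%, depending on which group is smaller). The text fixes 16 and 16.
- Smaller groups: 10 per group gives 83.3%. The text fixes 16.
- Different rates: 8% versus 48% gives 84.1%, and 17% versus 60% gives 83.6%. A mistyped rate is therefore possible.

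**Detectable difference at the stated level.** With the lower rate held at 8%, 84% power needs 48 − 8 = 40 points, against the 60 − 8 = 52 stated: 12 points fewer. With the upper rate held at 60%, it needs about 60 − 17 = 43 points: about 9 fewer.

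**The case against.** Four objections deserve weight.

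1. **The analysis is exploratory and the figure sized nothing.** The 32 is 80% of 40, and the 40 comes from the two-stage design. The correlative data are to be summarised mainly with descriptive statistics, and Section 13.3 treats subset analyses of correlatives as exploratory. This stands and limits the importance.
2. **If the stated level is right, the error is conservative.** The plan then claims less power than it has. This also stands, but only under that reading; if two-sided 0.05 was meant, the printed level is wrong.
3. **The match to two-sided 0.05 does not prove the origin.** One-sided 0.025 fits equally well, and a mistyped rate (48% in place of 60%, or 17% in place of 8%) would also give about 84% at one-sided 0.10. This is fair: where the 84% came from is inference.
4. **Other parts of the plan favour one-sided 0.10.** Section 13.3 uses it for response and toxicity, its two-sided 80% confidence intervals correspond to it, and the primary test is one-sided at 0.08. A planning slip in the correlative paragraph would not make the level for response and toxicity wrong. This stands too, and makes correcting the power figure the more natural repair.

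None of these makes 84% follow from the printed inputs, and nothing elsewhere in the documents explains the figure.

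**Conclusion.** The concern holds. For the test, level, rates and group sizes printed in Section 13, the power is 95.9%, not 84%: an error of 12 points that neither rounding nor choice of approximation explains. The printed 84% agrees with a two-sided 0.05 (one-sided 0.025) test of the same rates, at 83.9%. At least one of the power, the level or the rates is therefore misstated.

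The calculation rests only on printed inputs and on two independent binomial groups of 16. The 12-point overstatement of the detectable difference assumes that the lower rate stays at 8%. The primary response endpoint and the two-stage design are unaffected. This should be corrected, but it does not threaten the trial.

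**What to change.** Restate one consistent set in the correlative paragraph of Section 13:

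- **If one-sided 0.10 is intended** (the more natural reading): about 96% power for 8% versus 60%, with 16 per group. If 84% power is the wanted benchmark, give the rates as 8% versus 48%.
- **If two-sided 0.05 was intended:** keep 84% power for 8% versus 60%, state the two-sided 0.05 level, and say in Section 13.3 that the correlative comparisons use it. The level there for response and toxicity need not change on this account.

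Settle the level before the correlative data are examined. The cost is one sentence, plus a short clarification in Section 13.3 under the second option. Enrolment, biopsies and procedures do not change.
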